6.3.1.5. RT-PCR Confirmed Protocol-defined ILI Caused by Specific Influenza Strains

The other secondary endpoints defined in [Section 3.2.2](#) will be analyzed as follows:

- rVE of mRNA-1010 vs. the active comparator to prevent the occurrence of the first episode of RT-PCR confirmed protocol-defined ILI that begins at least 14 days after vaccination through Day 181 (Month 6) or at the end of the influenza season, whichever occurs later, caused by influenza A virus strain that is antigenically matched to the selected vaccine strain H1N1.
- rVE of mRNA-1010 vs. the active comparator to prevent the occurrence of the first episode of RT-PCR confirmed protocol-defined ILI that begins at least 14 days after vaccination through Day 181 (Month 6) or at the end of the influenza season, whichever occurs later, caused by influenza A virus strain that is antigenically matched to the selected vaccine strain H3N2.

- rVE of mRNA-1010 vs. the active comparator to prevent the occurrence of the first episode of RT-PCR confirmed protocol-defined ILI that begins at least 14 days after vaccination through Day 181 (Month 6) or at the end of the influenza season, whichever occurs later, caused by influenza A virus strains that are antigenically matched to the selected vaccine strains H1N1 and/or H3N2.

The first RT-PCR confirmed protocol-defined ILI caused by influenza A virus strain that is antigenically matched to the H1N1 strain contained in the vaccine:

- Must be the first RT-PCR confirmed protocol-defined ILI ([Section 6.3.1.1](#)),
- Antigenic match to the A/H1N1 strain contained in the vaccine must be confirmed using cultured viral isolate from the same NP swab sample by antigenicity testing with strain-specific reference sera.

Similarly, the first RT-PCR confirmed protocol-defined ILI caused by influenza A virus strain that is antigenically matched to the H3N2 strain contained in the vaccine are derived as:

- Must be the first RT-PCR confirmed protocol-defined ILI ([Section 6.3.1.1](#)),
- Antigenic match to the A/H3N2 strain contained in the vaccine must be confirmed using cultured viral isolate from the same NP swab sample by antigenicity testing with strain-specific reference sera.

The first RT-PCR confirmed protocol-defined ILI caused by influenza A virus strains that are antigenically matched to the selected vaccine strains H1N1 and/or H3N2 contained in the selected vaccine is derived similarly.

As for the key secondary efficacy endpoints, when a local certified laboratory is used for the RT-PCR test without a viral culture on the NP swab sample, then another qualified positive RT-PCR test with subsequent viral culture antigenic match result (positive or negative) can be used. The same search criteria (positive RT-PCR dates within 7 days) will be implemented.

The time to the first identified episode for each of these secondary efficacy endpoints, in days, will be calculated as: Start date of the first identified episode – Date of randomization + 1.

A participant will be counted as a culture-confirmed US CDC-defined ILI case caused by a specific influenza strain if the first identified episode for each of these secondary efficacy endpoints starts 14 days after the vaccination and up to Day 181 (Month 6) or at the end of the influenza season whichever occurs later, i.e.,

$$\text{Vaccination date} + 14 \leq \text{Start date of the first identified episode} \\ \leq \text{Date of Day 181/ Month 6 or at the end of the influenza season, whichever occurs later.}$$

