Culture-confirmed protocol-defined ILI is defined based on the following criteria:

1. The participant must have experienced the following symptoms: Body temperature $\geq 37.5^{\circ}\text{C}$ [$\geq 99.5^{\circ}\text{F}$] **accompanied by** at least **ONE** of respiratory illness symptom: sore throat, cough, sputum production, wheezing, or difficulty breathing.

AND

2. The participant must have a positive result for influenza infection by viral culture following a positive result for influenza infection by RT-PCR performed within 7 days after protocol-defined ILI symptom onset. Viral cultures will only be done on samples with a positive result for influenza infection by RT-PCR.

Culture-confirmed US CDC-defined ILI is defined based on the following criteria:

1. The participant must have experienced the following symptoms: Body temperature $\geq 37.8^{\circ}\text{C}$ [$\geq 100^{\circ}\text{F}$] **accompanied by** at least **ONE** respiratory illness symptom: cough, and/or sore throat.

AND

2. The participant must have a positive result for influenza infection by viral culture following a positive result for influenza infection by RT-PCR performed within 7 days after US CDC-defined ILI symptom onset. Viral cultures will only be done on samples with a positive result for influenza infection by RT-PCR.

RT-PCR confirmed ILI caused by specific influenza A strain

- rVE of mRNA-1010 vaccine vs. the active comparator to prevent the occurrence of the first episode of RT-PCR confirmed protocol-defined ILI that begins at least 14 days after vaccination through Day 181 (Month 6) or end of influenza season, whichever occurs later, caused by influenza A strain that is antigenically matched to the vaccine strain H1N1.
- rVE of mRNA-1010 vaccine vs. the active comparator to prevent the occurrence of the first episode of RT-PCR confirmed protocol-defined ILI that begins at least 14 days after vaccination through Day 181 (Month 6) or end of influenza season, whichever occurs later, caused by influenza A strain that is antigenically matched to the vaccine strain H3N2.
- rVE of mRNA-1010 vaccine vs. the active comparator to prevent the occurrence of the first episode of RT-PCR confirmed protocol-defined ILI that begins at least 14 days after vaccination through Day 181 (Month 6) or end of influenza season, whichever occurs later, caused by influenza A strain that is antigenically matched to the vaccine strain H1N1 and/or H3N2.

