For the definition of rVE and RT-PCR confirmed protocol-defined ILI definition, refer to the primary endpoint analysis in [Section 3.1.2](#). Furthermore, antigenic match to the selected vaccine A/H1N1 and/or A/H3N2 strains needs to be confirmed by antigenic testing using cultured viral isolate from the NP swab.

Hospitalizations associated with RT-PCR confirmed protocol-defined ILI

- rVE of mRNA-1010 vaccine vs. the active comparator to prevent hospitalizations associated with RT-PCR confirmed protocol-defined ILI that begins at least 14 days post vaccination through Day 181 (Month 6) or end of influenza season caused by any strain of influenza virus regardless of antigenic match to the strains selected for the seasonal vaccine.

The rVE is defined as the percent reduction in the risk of hospitalization associated with a RT-PCR confirmed protocol-defined ILI by the mRNA-1010 group, compared to active comparator group, i.e.

$$\text{rVE} = 100 \times (1 - \text{RR}) \%,$$

where RR is the relative risk between mRNA-1010 vs. active comparator. The RR will be estimated by ratio of the observed incidence rates in the two vaccine groups (mRNA-1010 vs. active comparator).

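### Does the counting sentence in SAP 6.3.1.5 turn the strain-specific endpoints into CDC-defined illness and so drop cases?

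*SAP*

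**What the plan says.** SAP 3.2.2 defines three endpoints on RT-PCR confirmed protocol-defined ILI. One is "caused by influenza A strain that is antigenically matched to the vaccine strain H1N1"; the second does the same for H3N2, and the third accepts either strain. The text below them states which illness definition applies: "For the definition of rVE and RT-PCR confirmed protocol-defined ILI definition, refer to the primary endpoint analysis". It adds the laboratory condition: "antigenic match to the selected vaccine A/H1N1 and/or A/H3N2 strains needs to be confirmed by antigenic testing using cultured viral isolate from the NP swab".

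SAP 6.3.1.5 is headed "RT-PCR Confirmed Protocol-defined ILI Caused by Specific Influenza Strains". For H1N1 and for H3N2 it gives two derivation rules. The episode "Must be the first RT-PCR confirmed protocol-defined ILI", and the match "must be confirmed using cultured viral isolate from the same NP swab sample by antigenicity testing with strain-specific reference sera". The either-strain endpoint is derived in the same way.

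The section then says how a participant is counted. The label given to the case is: "A participant will be counted as a culture-confirmed US CDC-defined ILI case caused by a specific influenza strain". The condition attached to that label concerns timing alone, namely "if the first identified episode for each of these secondary efficacy endpoints starts 14 days after the vaccination"; the window closes on Day 181 or when the season ends, whichever is later. An inequality on dates restates that window.

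SAP 6.3.1.7 provides hazard ratios with 95% confidence intervals for the other secondary endpoints. It censors at illness onset when an extra condition of an endpoint is not met, and states that these analyses are outside multiplicity control.

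**The concern.** The words in the counting sentence are a defined term. SAP 3.2.2 and 6.3.1.4 set out culture-confirmed CDC-defined ILI as a secondary endpoint of its own. It requires at least 37.8 °C with cough and/or sore throat. Protocol-defined ILI requires at least 37.5 °C with any one of five respiratory symptoms.

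One section therefore appears to hold two rules with different case sets. If the counting sentence governed, a matched case at 37.6 °C, or one with only sputum, wheeze or difficulty breathing, would meet the endpoint definition yet not be counted. The censoring rule in SAP 6.3.1.7 could then turn that event into a censored observation. Three strain-specific estimates would rest on fewer events and a narrower illness than their titles state.

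**Working it through.** The documents give no case count, power or sample size for these endpoints, so there is no planned figure to reproduce. The check compares the texts and then sizes the misreading.

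**1. Which illness definition each place uses**

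| Place | Illness named |
|---|---|
| SAP 3.2.2, three endpoint definitions | RT-PCR confirmed protocol-defined |
| SAP 3.2.2, cross-reference to the primary endpoint | RT-PCR confirmed protocol-defined |
| SAP 6.3.1.5, heading and three bullets | RT-PCR confirmed protocol-defined |
| SAP 6.3.1.5, derivation rules | RT-PCR confirmed protocol-defined, plus antigenic match |
| SAP 6.3.1.5, counting sentence (label) | culture-confirmed CDC-defined |
| SAP 6.3.1.5, counting sentence (condition) and inequality | onset date only |

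Only the label disagrees. It matches the endpoint of the preceding section, 6.3.1.4. In 6.3.1.3 and 6.3.1.4 the parallel sentence names that section's own endpoint, so carried-over text is the likely explanation. That is an inference.

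**2. What the sentence tests.** Its condition asks whether the first identified episode for these endpoints falls in the window. That episode is the one fixed by the derivation rules: protocol-defined, with a matched isolate. Section 6.3.1.5 contains no 37.8 °C threshold and no requirement for cough or sore throat. Cases removed when the section is followed: 0.

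**3. What the label would remove if used as a filter.** Consider the two temperature bands that qualify (37.5 to below 37.8 °C; 37.8 °C and above) and every non-empty set of the five symptoms.

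- Qualifying profiles: 2 × (2⁵ − 1) = 62.
- Failing the culture part: 0, because an antigenic match already needs a cultured isolate.
- Failing the CDC part: all 31 in the lower band, plus 2³ − 1 = 7 in the upper band with neither cough nor sore throat, giving 38.
- CDC-defined profiles outside the protocol definition: 0.

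These count profiles, not patients. They show that a filter could only remove cases, and only through fever and symptoms.

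**4. Cost of that filter.** The share *x* of matched cases failing the CDC definition is not given, so it is assumed. The standard error of the log hazard ratio rises by 1/√(1 − x) − 1:

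| x | Rise in standard error |
|---|---|
| 0 | 0% |
| 0.10 | 5.4% |
| 0.20 | 11.8% |
| 0.30 | 19.5% |
| 0.40 | 29.1% |

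For scale, take the 365 planned per-protocol cases in SAP 4.3 and assume that 25% to 75% are matched. With x = 0.40 the filter would remove between 365 × 0.25 × 0.40 ≈ 36 and 365 × 0.75 × 0.40 ≈ 110 events. With x = 0 it would remove none.

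**5. Whether the censoring rules supply the filter.** SAP 6.3.1.7 censors on conditions that the endpoint requires. Here the required addition is antigenic match on a cultured isolate (3.2.2 and 6.3.1.5), not CDC symptoms. The row of Table 14 (Appendix I) for events that miss an endpoint's own definition names the CDC-defined and culture-confirmed endpoints, not the strain-specific ones. Its list is introduced as open, but even if it were extended to these endpoints, their own definition is the protocol one. Unknown match status has a separate row.

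**The case for a change.** The best case for a change is that the SAP alone must settle the matter. The protocol's secondary endpoints do not include the H1N1- and H3N2-matched ones, and the SAP states that it prevails over the protocol on methods. A programmer who took the label at face value would find a row in Table 14 naming that very endpoint and could apply it. Even with correct programming, a table titled from this sentence would call protocol-defined cases CDC-defined. The correction is one phrase.

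Part of this stands: the label is wrong, neither text extraction nor redaction explains it, and output titles should follow 3.2.2. The route to lost cases does not stand. It requires overriding the endpoint definition, its cross-reference, the section heading and the derivation rules in favour of one noun phrase whose own condition points back to those rules. An analyst who has to derive the episode before dating it will already have applied the protocol definition.

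The worry that these estimates would no longer be comparable with the primary endpoint is also weak. They count only matched influenza A, and cases with unknown match are censored, so they do not partition the primary cases under either reading. The breakdown of protocol-defined ILI by RT-PCR subtype is a separate supportive analysis in SAP 6.3.1.2.3, which this sentence does not affect.

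**Conclusion.** This is a clerical slip. The counting sentence carries the wrong case label, but the case set is fixed by the definitions in SAP 3.2.2 and the derivation rules in 6.3.1.5, and following them loses no case. The 5% to 29% rise in standard error belongs to a filter that the plan does not contain, and its inputs are assumptions.

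The reach is small in any event. The three endpoints are estimated with confidence intervals, without multiplicity control and without formal testing (SAP 6.3.1.7 and 6.5.2). The primary and key secondary endpoints, the alpha allocation, the sample size and the power do not depend on this sentence. Tidying the label would be sensible housekeeping, but it would alter no case set, estimate or conclusion, so no change to the plan follows. This rests on programmers working from the derivation rules, which is how the section is built.

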6.3.1.6. Hospitalizations Associated with RT-PCR Confirmed Protocol-Defined ILI

This secondary efficacy endpoint is the rVE of mRNA-1010 vs. the active comparator in preventing hospitalizations associated with RT-PCR confirmed protocol-defined ILI starting 14 days post vaccination through Day 181 (Month 6) or at the end of the influenza season, whichever occurs later, caused by any strain of influenza virus regardless of antigenic match to the strains selected for the seasonal vaccine.

Cases of hospitalizations associated with a protocol-defined ILI will be identified in the Adverse Events Healthcare Encounter eCRF page if the reason for the hospitalization is assessed to be associated with a protocol-defined ILI by the investigator. These cases will be adjudicated by a blinded medical team before database lock and will be verified for confirmation by a positive RT-PCR test.

Participants with at least one hospitalization associated with a RT-PCR confirmed ILI that starts 14 days after the vaccination and up to Day 181 (Month 6) or at the end of the influenza season whichever occurs later will be summarized based on the PP Set.

6.3.1.7. Analysis of Other Secondary Efficacy Endpoints

For each of the other secondary efficacy endpoints discussed in [Section 6.3.2.3.1 – 6.3.2.3.4](#), a stratified Cox proportional hazards model will be used to estimate the HR. Relative vaccine efficacy will be estimated along with two-sided 95% CI based on the PP and mITT Sets.

Intercurrent events, missing data, and censoring rules will be similar to those for the primary and key secondary efficacy endpoints, where applicable. After the first RT-PCR confirmed protocol-defined ILI is identified, if any additional condition required for the other efficacy endpoint is not met or cannot be determined, the observation will be censored at the ILI start date for the corresponding other secondary efficacy endpoints.

The other secondary efficacy endpoint discussed in [Section 6.3.2.3.5](#) will be analyzed as follows:

- rVE of mRNA-1010 vs. the active comparator in preventing hospitalizations associated with RT-PCR confirmed protocol-defined ILI starting 14 days post vaccination through Day 181 (Month 6) or the end of the influenza season, whichever occurs later, caused by any strain of influenza virus regardless of antigenic match to the strains selected for the seasonal vaccine

The number and percentage of participants with at least one case will be summarized by vaccination group.

The rVE will be estimated by one minus the ratio of observed incidence rates (mRNA-1010 vs. active comparator) multiplied by 100%:

$$\text{rVE} = 100 \times (1 - [(C_{\text{mRNA}}/N_{\text{mRNA}}) / (C_{\text{control}}/N_{\text{control}})]) \%,$$

where C_{mRNA} and $C_{control}$ are the number of cases per the hospitalizations associated with RT-PCR confirmed protocol-defined ILI efficacy endpoint definition in the mRNA-1010 group and the active comparator group respectively, and N_{mRNA} and $N_{control}$ are the number of participants in the mRNA-1010 group and the active comparator group, respectively.

A 2-sided 95% CI for rVE will be calculated based on Farrington and Manning's score method ([Farrington and Manning 1990](#)) based on the PP and mITT Sets.

The above analyses of secondary efficacy endpoints are not controlled for multiplicity.

6.4. Immunogenicity Analyses

The primary analysis population for immunogenicity will be the PP Immunogenicity Subset. For all summary tables, antibody titers reported as below the lower limit of quantification (LLOQ) will be replaced by $0.5 \times \text{LLOQ}$. Values that are greater than the upper limit of quantification (ULOQ) will be converted to the ULOQ.

For each of the four strains, the GMT of HAI titers with corresponding 95% CI will be provided at each time point. The 95% CIs will be calculated based on the t-distribution of the log-transformed values then back transformed to the original scale. The GMFR of HAI titers with corresponding 95% CI at Day 29 over baseline will also be provided.

Descriptive summary statistics will also be provided, including n, median, minimum, and maximum will be provided.

An analysis of covariance (ANCOVA) model will be carried out. The model will include the log-transformed HAI titers at Day 29 as the dependent variable, vaccination group as the fixed variable, log-transformed baseline HAI titers as a fixed covariate, adjusting for the stratification factors. The geometric least square mean (GLSM), and its corresponding 95% CI results on the log-transformed scale estimated from the model will be back-transformed to obtain these estimates on the original scale, as an estimate of the GMT. GMR, estimated by the ratio of GLSM and the corresponding two-sided 95% CI will be provided to assess the difference in immune response between the mRNA-1010 compared to the active comparator group at Day 29.

For each strain, seroconversion is defined as either a pre-vaccination HAI titer < 1:10 and a post-vaccination titer \geq 1:40 or a pre-vaccination HAI titer \geq 1:10 and a minimum four-fold rise in post-vaccination HAI antibody titer.

The number and percentage of participants with seroconversion due to vaccination will be provided with two-sided 95% CI using the Clopper-Pearson method at Day 29. To compare the seroconversion rates between the vaccination groups, the Miettinen-Nurminen method will be used to calculate the 95% CI for the difference in seroconversion rates. The seroconversion rate difference with the corresponding 95% CI at Day 29 will be provided for each strain.

In addition, the number and percentage of participants with an HAI titer \geq 1:40 post-injection due to vaccination will be provided with two-sided 95% CI using the Clopper-Pearson method.

The above immunogenicity analyses will be repeated using the Immunogenicity Subset as a sensitivity analysis.

Subgroup analyses will be performed in the Per-Protocol Immunogenicity Subset for the following subgroups: Age Group 1, Age Group 2, Prior Influenza Vaccine Status, Sex, Race, and Ethnicity ([Section 6.1.8](#)). Subgroups with fewer than 30 participants in the analysis set may be combined in other subgroups.

6.5. Planned Analyses

There is one planned IA with data cut-off around the middle of February 2023 regardless of number of influenza cases accrued for the primary NI hypothesis to be tested to support the primary objective. The intent of the IA is for early detection of reliable evidence that rVE of mRNA-1010 is noninferior to the active comparator. The Lan-DeMets Pocock boundaries are used for calculating efficacy boundaries and to preserve the (1-sided) 2.5% Type I error rate over the IA and the final analysis (when the target number of cases have been observed), relative to the hypothesis:

$$H_0^1: HR \geq 1.1 \text{ (equivalently, rVE} \leq -10\%).$$

If NI is demonstrated at an IA, the subsequent final analysis will be considered supportive in nature for the NI claim. The DSMB will review the IA results and make recommendations to the Sponsor in terms of study results reporting and unblinding based on the boundaries of early efficacy as described in this section.

In summary, one IA for the primary efficacy endpoints and a final efficacy analysis are planned in this study ([Table 4](#)). An EoS analysis may be performed in this study as described below.

- IA for the primary efficacy endpoint will be performed with data cut-off around the middle of February 2023 when it is projected that approximately 75% of the total cases (274 RT-PCR confirmed protocol-defined ILI cases across both treatment groups) would be observed in the PP Set. In the case that fewer cases are observed by middle of February, the IA will continue to be conducted during this timeframe due to seasonality considerations. The nominal alpha level to be spent at the IA and final analysis will be adjusted accordingly. The DSMB will review the unblinded IA results.
- The final efficacy analysis will be performed when approximately 365 cases across both treatment groups have been observed in the PP set.
- The EoS analysis may be performed when all study participants have completed the final visit on Day 361 (Month 12) or have withdrawn from the study. The study database will be cleaned and locked, and the study will be unblinded.

The RT-PCR confirmed ILI cases are counted when the first episode starts 14 days after the vaccination and up to Day 181/ Month 6 or at the end of the influenza season whichever ends later.

Table 4: Planned Analyses and Hypothesis Testing for the Primary Efficacy Endpoint

| Planned Analysis | Noninferiority testing on PP Set | Superiority testing on mITT Set |
|-----------------------|----------------------------------|---------------------------------|
| IA (75%) | 274 cases | 290 cases |
| Final Analysis (100%) | 365 cases | 386 cases |

Subsequent final analysis is of a supportive nature if success is achieved at the IA.

